10. APPENDICES

10.1. Appendix 1: Protocol Deviation Management

- Protocol deviations will be tracked by the study team throughout the conduct of the study in accordance with the Protocol Deviation Management Plan.
 - o Data will be reviewed prior to freezing the database to ensure all important deviations are captured and categorised on the protocol deviations dataset.
 - This dataset will be the basis for the summaries and listings of protocol deviations.

10.2. Appendix 2: Schedule of Activities

10.2.1. Protocol Defined Schedule of Events

Procedure	Screening (up to 28 days before Day	Trea	tment Perio Da	Follow-up Visit (7 to 9 days post last dose)	Notes		
	1)	-1	1	2	3		
Informed consent	X						
Inclusion and exclusion criteria ¹	Х						Recheck clinical status before 1st dose of study medication.
Demography	Х						
Full physical examination including height and weight	Х						
Brief physical examination		х		X2	X2	х	Discharge (48 h post-dose for Part B, and Treatment Periods 1, 2, 4, 5 and 6 for Part A; 24 h post-dose for Part A Treatment Period 3 only)
Medical history (includes substance usage) ³	Х	×					Substances: Drugs, Alcohol, tobacco and caffeine
Past and current medical conditions	X						
Follicle Stimulating Hormone (FSH) and estradiol (as needed in women of non-childbearing potential only)	Х						
Serum pregnancy test (WOCBP)	х	9				х	

Procedure	Screening (up to 28 days before Day	Tre	atment Perio Da	The second second	i, 6	Follow-up Visit (7 to 9 days post last dose)	Notes
	1)	-1	1	2	3	- 4000)	
Urine pregnancy test (WOCBP)		х		X4	X4		4. Discharge (48 h post-dose for Part B, and Treatment Periods 1, 2, 4, 5 and 6 for Part A; 24 h post-dose for Part A Treatment Period 3 only)
Human Immunodeficiency Virus (HIV), Hepatitis B and C screening ⁵	х						If test otherwise performed within 3 months prior to first dose of study treatment, testing at screening is not required
Tuberculosis (TB) Test	X						
Urine drug screen	х	X					
Alcohol breath test	х	X					
Carbon monoxide breath test	Х	Х)				
Laboratory assessments (haematology, clinical chemistry and urinalysis)	х	X6		X7		х	Results must be available prior to dosing on Day 1 24 h post-dose Allowable windows in Section 9.4.4
Glomerular filtration rate	X						
C-reactive protein (CRP)	Х						

Procedure	Screening (up to 28 days before Day	Tre	atment Period Day		, 6	Follow-up Visit (7 to 9 days post last dose)	Notes
	1)	-1	1	2	3		
12-lead ECG	X8	Х	Xa	X ¹⁰		х	In triplicate Pre-dose and 2 and 12 h post-dose Allowable windows in Section 9.4.3
Vital signs	х	Х	Χιι	X12. 13	X13	х	11. Pre-dose and 2 and 12 h post-dose 12. 24 h post-dose Allowable windows in Section 9.4.2 13. Discharge (48 h post-dose for Part B, and Treatment Periods 1, 2, 4, 5 and 6 for Part A; 24 h post-dose for Part A Treatment Period 3 only)
Genetics blood sample collection (optional)			X14				14. A blood sample is collected at the Day 1 visit, after the participant has been randomised and provided informed consent for genetic research. If the sample is not collected on Day 1, it can be collected at any time during the study after randomization. Subjects that decline to provide a sample will still be eligible for this study

Procedure	Screening (up to 28 days before Day	Tre	atment Period Day		, 6	Follow-up Visit (7 to 9 days post last dose)	Notes
	1)	-1	1	2	3	4000/	
Study treatment			X				
AE review		←====				=========	
Serious AE (SAE) review	X	←====				========	
Concomitant medication review		-===			===>		
PK blood sample collection			X15	X15	X15		15. Time points in Table 2

Table 2 from Protocol

	£					Treat	ment Per	riods 1,	2, 4, 5 ar	d 6 (MR	Formu	lations)	and Part	B (All P	eriods)					
Time	Pre- dose	0 h	2 h	4 h	6 h	8 h	10 h	12 h	14 h	16 h	18 h	20 h	22 h	24 h	26 h	28 h	30 h	32 h	36 h	48 h
Dosing		Χ							1				9							8
PK sampling	X		X	X	X	X	X	X	X	X	X	X	X	X	X	X	X	X	X	X
	35	85	331		8	45	Part	A: Treat	ment Pe	riod 3 (I	R Form	ulation)	43	2%	92		18	33	33	-
Time	Pre- dose	0 h		0.33 h	0.66 h	1 h	1.5	h	2 h	3 h		4 h	5 h	6 h		8 h	10 h	121	h	24 h
Dosing		X									- 6								80	
PK sampling	X			X	X	X	X		X	X	0	X	X	X	1	X	X	X		X

10.3. Appendix 3: Assessment Windows

10.3.1. Definitions of Assessment Windows for Analyses

No Assessment Windows will be defined for Analysis, and summaries and analyses will be based on nominal visits.

10.4. Appendix 4: Study Phases and Treatment Emergent Adverse Events

10.4.1. Study Phases

Assessments and events will be classified according to the time of occurrence relative to dosing.

Treatment Phase	Definition
Pre-Treatment	Date ^[1] ≤ Study Treatment Start Date ^[1]
On-Treatment	Study Treatment Start Date ^[1] < Date ^[1] ≤ Study Treatment Stop Date ^[1]
Post-Treatment	Date ^[1] > Study Treatment Stop Date ^[1]

^[1] Datetime if Time is present for assessments or events

10.4.1.1. Study Phases for Concomitant Medication

Study Phase	Definition
Prior	If medication end date is not missing and is before 28 days prior to screening visit
Concomitant	Any medication that is not a prior

NOTES:

 Please refer to Appendix 7: Reporting Standards for Missing Data for handling of missing and partial dates for concomitant medication. Use the rules in this table if concomitant medication date is completely missing.

10.4.2. Treatment Emergent Flag for Adverse Events

Flag	Definition
Treatment Emergent	 If AE onset date is on or after treatment start date & on or before treatment stop date. (plus washout or protocol-specified time limit (e.g. half-life of drug, certain number of days, etc.). Study Treatment Start Date ≤ AE Start Date ≤ Study Treatment Stop Date.
	 For studies with greater than one treatment period (e.g., crossover study), if AE onset is during one period and worsens during a later period it would be counted in both periods. For the initial period the logic would be as above. For the later period the logic would use the treatment dates associated with the later period: Treatment Period Start Date ≤ AE Worsening Date ≤ Study Treatment Stop Date.

NOTES:

- If the study treatment stop date is missing, then the AE will be considered to be On-Treatment.
- Time of study treatment dosing and start/stop time of AEs should be considered, if collected.

10.5. Appendix 5: Data Display Standards & Handling Conventions

10.5.1. Reporting Process

Software				
The currently supplementary	ported versions of SAS software and WIN-NonLin will be used.			
Reporting Area				
HARP Server	: UK1SALX00175			
HARP Area	Final			
	: \arprod\gsk2982772\ mid209261\final_01			
QC Spreadsheet	: \arwork\gsk2982772\mid209261\final_01\documents			
Analysis Datasets				
Analysis datasets will be created according to Legacy GSK Integrated Data Standards Library (IDSL) A&R dataset standards.				
Generation of RTF Files				
RTF files will be generated for SAC tables.				

10.5.2. Reporting Standards

General

- The current GSK Integrated Data Standards Library (IDSL) will be applied for reporting, unless otherwise stated (IDSL Standards Location: https://spope.gsk.com/sites/IDSLLibrary/SitePages/Home.aspx):
 - 4.03 to 4.23: General Principles
 - 5.01 to 5.08: Principles Related to Data Listings
 - 6.01 to 6.11: Principles Related to Summary Tables
 - 7.01 to 7.13: Principles Related to Graphics
- Do not include subject level listings in the main body of the GSK Clinical Study Report. All subject level listings should be located in the modular appendices as ICH or non-ICH listings

Formats

- GSK IDSL Statistical Principles (5.03 & 6.06.3) for decimal places (DP's) will be adopted for reporting of data based on the raw data collected, unless otherwise stated.
- Numeric data will be reported at the precision collected on the eCRF.
- The reported precision from non eCRF sources will follow the IDSL statistical principles but may be adjusted to a clinically interpretable number of DP's.
 - PK Summary Statistics: 3 significant figures for the lowest value of each PK parameter.
 The summary statistics for higher values will be reported to the same number of decimal places as the lowest value

Planned and Actual Time

- Reporting for tables, figures and formal statistical analyses:
 - Planned time relative to dosing will be used in figures, summaries, statistical analyses and calculation of any derived parameters, unless otherwise stated.
 - The impact of any major deviation from the planned assessment times and/or scheduled visit days on the analyses and interpretation of the results will be assessed as appropriate.
- Reporting for Data Listings:
 - Planned and actual time relative to study drug dosing will be shown in listings (Refer to IDSL Statistical Principle 5.05.1).

 Unscheduled or unplanned readings will be presented within the subject's listings. 					
Unscheduled Visits					
 Unscheduled visits 	s will not be included in summary tables and/or figures, except where appropriate.				
All unscheduled vis	sits will be included in listings.				
Descriptive Summary	Statistics				
Continuous Data	Refer to IDSL Statistical Principle 6.06.1				
Categorical Data	Categorical Data N, n, frequency, %				
Graphical Displays	Graphical Displays				
Refer to IDSL Statistical Principals 7.01 to 7.13.					
Reporting of Pharmacokinetic Concentration Data					
Descriptive Summary Refer to IDSL Statistical Principle 6.06.1					
Statistics	Assign zero to NQ values (Refer to GUI_51487 for further details)				

10.6. Appendix 6: Derived and Transformed Data

10.6.1. General

Multiple Measurements at One Analysis Time Point

- Mean of the measurements will be calculated and used in any derivation of summary statistics but if listed, all data will be presented.
- If there are two values within a time window (as per Section 10.3.1) the value closest to the target day for that window will be used. If values are the same distance from the target, then the mean will be taken.
- Participants having both High and Low values for Normal Ranges at any post-baseline visit for safety parameters will be counted in both the High and Low categories of "Any visit post-baseline" row of related summary tables. This will also be applicable to relevant Potential Clinical Importance summary tables.

Study Day

- Calculated as the number of days from First Dose Date:
 - Ref Date = Missing → St
 - → Study Day = Missing
 - Ref Date < First Dose Date → Study Day = Ref Date First Dose Date
 - Ref Data ≥ First Dose Date → Study Day = Ref Date (First Dose Date) + 1

10.6.2. Study Population

Demographics

Date of Birth

Only the year of birth will be captured, and therefore the date of birth is then derived as follows:
 Year of birth = YYYY → Date of birth = 30th June YYYY

Age

- Calculated as the integer part of (date of screening date of birth)
 Age = integer part (date of screening 30th June YYYY)/365.25.
- Birth date will be presented in listings as 'YYYY'.

Body Mass Index (BMI)

Calculated as Weight (kg) / [Height (m)²]

Treatment Compliance

• Treatment compliance will be calculated based on the formula:

Treatment Compliance = Number of Actual Doses / (Planned Treatment Duration in Days * Frequency)

• Frequency is 2 for BID and 1 for QD. Treatment compliance could be greater than 100% if there are events of overdose. Cumulative compliance (since Day 1) at each visit will be calculated.

Extent of Exposure

Number of days of exposure to study drug will be calculated based on the formula:

Treatment Compliance

Duration of Exposure in Days = Treatment Stop Date - (Treatment Start Date) + 1

- Participants who were randomized but did not report a treatment start date will be categorised as having zero days of exposure.
- The cumulative dose will be based on the formula:

Cumulative Dose = Sum of (Number of Days x Total Daily Dose)

If there are any treatment breaks during the study, exposure data will be adjusted accordingly.

10.6.3. Efficacy

N/A

10.6.4. Safety

ECG Parameter

RR Interval

- IF RR interval (msec) is not provided directly, then RR can be derived as :
 - [1] If QTcB is machine read & QTcF is not provided, then:

$$RR = \left[\left(\frac{QT}{QTcB} \right)^2 \right] * 1000$$

[2] If QTcF is machine read and QTcB is not provided, then:

$$RR = \left[\left(\frac{QT}{QTcF} \right)^3 \right] * 1000$$

• If ECGs are manually read, the RR value preceding the measurement QT interval should be a collected value THEN do not derive.

Corrected QT Intervals

- When not entered directly in the eCRF, corrected QT intervals by Bazett's (QTcB) and Fridericia's (QTcF) formulas will be calculated, in msec, depending on the availability of other measurements.
- IF RR interval (msec) is provided then missing QTcB and/or QTcF will be derived as

$$QTcB = \frac{QT}{\sqrt{\frac{RR}{1000}}} \qquad QTcF = \frac{QT}{3\sqrt{\frac{RR}{1000}}}$$

ECG Parameter	Units	QTc Categories			
		Lower	Upper		
Absolute					
Absolute QTc Interval		≤ 450			
		> 450	≤ 480		
	msec	> 480	≤ 500		
		> 500			
Change from Baseline					

ECG Parameter	Units	QTc Categories		
		Lower	Upper	
		≤ 30		
Increase from Baseline QTc	msec	> 30	≤ 60	
		> 60		

See Section 8.1.2 of the protocol for QTc stopping criteria. In addition to the two stopping criteria outlined in the protocol,

- QTc >500 msec
- Change from baseline (pre-dose Day 1) of QTc >60 msec

a third criteria will be flagged for summary purposes:

• Change from triplicate screening of QTc >60 msec

Laboratory Parameters

- If a laboratory value which is expected to have a numeric value for summary purposes, has a non-detectable level reported in the database, where the numeric value is missing, but typically a character value starting with '<x' or '>x' (or indicated as less than x or greater than x in the comment field) is present, the number of decimal places in the observed values will be used to determine how much to add or subtract in order to impute the corresponding numeric value.
 - Example 1: 2 Decimal Places= '< x ' becomes x 0.01
 - Example 2: 1 Decimal Places = '> x' becomes x + 0.1
 - Example 3: 0 Decimal Places = '< x' becomes x 1

10.6.5. Pharmacokinetic

The pharmacokinetic parameters will be calculated by standard non-compartmental analysis according to current working practices using WinNonlin Version 6.3 or higher.

Pharmacokinetic Endpoints

AUC(0-t)

Area under the concentration-time curve from time zero to the time of the last quantifiable concentration
(C(t)) will be calculated using the linear trapezoidal rule for each incremental trapezoid and the log
trapezoidal rule for each decremental trapezoid.

AUC(0-∞)

• Area under the concentration-time curve extrapolated to infinity will be calculated as:

$$AUC = AUC(0-t) + C(t) / lambda_z$$

where lambda z is the terminal phase rate constant.

Pharmacokinetic Endpoints

AUC(0-24)

Area under the concentration-time curve from time zero to 24 h post dose will be calculated using the linear trapezoidal rule for each incremental trapezoid and the log trapezoidal rule for each decremental trapezoid.

AUC%extrap

Percentage of AUC extrapolated beyond the last measured time point

C_{max}

Maximum observed concentration, determined directly from the concentration-time data

C_{24h}

Observed concentration at 24 hours, determined directly from the concentration-time data

Tmax

Time to reach Cmax, determined directly from the concentration-time data.

Tlast

Time of last measurable concentration

Tlag

Time from dosing at which GSK2982772 was first quantifiable in a concentration vs time profile

t1/2

Terminal half-life

Notes

Additional parameters may be included as required

Relative Bioavailability (Frel)

• Frel will be calculated as follows:

$$Frel = \frac{GeoMean\{AUC\ or\ C_{max}(test)\}}{GeoMean\{AUC\ or\ C_{max}(reference)\}} \times 100$$
Fred will be calculated using AUC on AUC (0 less). Given and

Frel will be calculated using AUC_(0-inf), AUC(0-last), C_{24h}, and C_{max}.

- MR Formulation (test) vs IR Formulation (reference)
- MR Fed (test) vs MR Fasted (reference)
- Enteric Coated (test) vs MR (reference)

MR refers to DiffCORE

10.7. Appendix 7: Reporting Standards for Missing Data

10.7.1. Premature Withdrawals

Element	Reporting Detail
General	Subject study completion (i.e. as specified in the protocol) was defined as one who completes all phases of the study including the last scheduled procedure shown in the SoA i.e. the follow-up visit.
	Withdrawn subjects may be replaced in the study.
	All available data from participants who were withdrawn from the study will be listed and all available planned data will be included in summary tables and figures, unless otherwise specified.

See study protocol for liver chemistry, QTc, and nervous system early stopping criteria.

10.7.2. Handling of Missing Data

Element	Reporting Detail
General	Missing data occurs when any requested data is not provided, leading to blank fields on the collection instrument:
	 These data will be indicated by the use of a "blank" in subject listing displays. Unless all data for a specific visit are missing in which case the data is excluded from the table.
	 Answers such as "Not applicable" and "Not evaluable" are not considered to be missing data and should be displayed as such.
Outliers	Any participants excluded from the summaries and/or statistical analyses will be documented along with the reason for exclusion in the clinical study report.

10.7.2.1. Handling of Missing and Partial Dates

Element	Reporting Detail
General	Partial dates will be displayed as captured in subject listing displays.
Adverse Events	 The eCRF allows for the possibility of partial dates (i.e., only month and year) to be recorded for AE start and end dates; that is, the day of the month may be missing. In such a case, the following conventions will be applied for calculating the time to onset and the duration of the event: Missing Start Day: First of the month will be used unless this is before the start date of study treatment; in this case the study treatment start date will be used and hence the event is considered On-treatment as per Appendix 4: Study Phases and Treatment Emergent Adverse Events. Missing Stop Day: Last day of the month will be used, unless this is after the stop date of study treatment; in this case the study treatment stop date will be used. Completely missing start or end dates will remain missing, with no imputation applied. Consequently, time to onset and duration of such events will be missing.
Concomitant Medications/ Medical History	 Partial dates for any concomitant medications recorded in the CRF will be imputed using the following convention: If the partial date is a start date, a '01' will be used for the day and 'Jan' will be used for the month If the partial date is a stop date, a '28/29/30/31' will be used for the day (dependent)

Element	Reporting Detail
	on the month and year) and 'Dec' will be used for the month.
	The recorded partial date will be displayed in listings.

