5.1.1. Part A

Part A of the study is a non-randomised up to 6 period, 6-way fixed sequence design in which up to 4 MR tablet prototype coated formulations may be evaluated following single dose administration in the fasted state (240 mg) (Figure 1). Periods 1, 2 and 3 will evaluate MR1 (similar in vitro dissolution to the slowest minitab MR formulation from study 205017), IR Tablet (240 mg) and MR2 (slower in vitro dissolution than MR1) respectively. Periods 4, 5 and 6 will be flexible and the dosing regimen will be dependent on the outcome of Periods 1 to 3. In Periods 4 to 6, there will be the option to optimise the MR release duration and evaluate the impact of a high-fat meal of one or more already studied MR formulations. In addition, the impact of food (standard breakfast or administration 30 or 60 minutes before a standard breakfast) on selected MR prototype coated tablet formulations may also be evaluated in Period 5 or 6, as applicable. There will also be the option to cancel Periods 5 and 6 if an optimal formulation is determined in Periods 1 or 3 which shows no clinically significant food effect with a high-fat meal in Period 4. There will be interim decisions after Periods 3, 4 and 5, where appropriate, to determine the formulations and prandial status to be investigated in the next period. Following the final period of Part A, there will be an interim review to determine whether to proceed with optional Part B, and if so, the formulations and tablet strengths to be investigated in Part B.

Each inpatient period for the MR regimens (Periods 1, 3, 4 to 6) will consist of 4 days and 3 nights, and the inpatient period for the IR tablet (Period 2) will consist of 3 days and 2 nights. There will be a minimum washout of 7 days between doses, and a follow-up visit will occur at 7 to 9 days after the last study treatment. Participants will receive a single oral dose of study treatment during each inpatient period.

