4. ANALYSIS POPULATIONS

Population	Definition / Criteria	Analyses Evaluated
All Subjects	 All participants who were screened for eligibility and allocated a subject number. 	Selected Study Population
Safety	All participants who receive at least 1 dose of study	 Safety and Study

Population	Definition / Criteria	Analyses Evaluated
	treatment and will be the population for reporting of safety and study population data. Participants will be analyzed according to the treatment they actually received.	Population
PK	Participants in the 'Safety Population' for whom a PK sample was obtained and analysed will be the population for reporting of PK data.	• PK

Refer to Appendix 10: List of Data Displays which details the population used for each display.

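### SAP 10.7.2.1 floors an imputed AE start day at the first dose of the study only, so in this multi-period design most imputed onsets would precede the dose of the AE's own period

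*SAP*

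**What the plan says.** SAP 10.7.2.1 (Handling of Missing and Partial Dates) notes that month-only AE dates can occur: "The eCRF allows for the possibility of partial dates (i.e., only month and year) to be recorded for AE start and end dates". It states the purpose of its conventions: "the following conventions will be applied for calculating the time to onset and the duration of the event". The start-day rule is "Missing Start Day: First of the month will be used unless this is before the start date of study treatment"; where the first of the month is earlier than that, "in this case the study treatment start date will be used and hence the event is considered On-treatment as per Appendix 4".

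Appendix 4 (SAP 10.4.1) works by date: "Assessments and events will be classified according to the time of occurrence relative to dosing". Its treatment-emergent flag (SAP 10.4.2) uses study-level start and stop dates for the initial period. For an AE that worsens in a later period it uses a separate, period-level term: "Treatment Period Start Date ≤ AE Worsening Date ≤ Study Treatment Stop Date". That term does not appear in the start-day rule.

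On the design, Protocol 5.1.1 says "There will be a minimum washout of 7 days between doses", with one single dose in each period. Part A has up to 6 periods and Part B up to 7, in a fixed sequence. SAP Section 4 says of the Safety population: "Participants will be analyzed according to the treatment they actually received".

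**The concern.** First-of-month imputation with a study-level floor suits a trial with one continuous treatment. Here one calendar month can hold four or five different regimens. The imputed date can never be later than the true onset, and from Period 2 onward the floor lies before the dose that the AE followed.

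An invented example: doses on 5, 12, 19 and 26 March, and an AE starting on 27 March with the day missing. The first of the month precedes the first dose, so the onset becomes 5 March. Measured from its own dose, time to onset is -21 days instead of 1. With a known stop date, duration is overstated by 22 days.

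The error has one direction and the sequence is the same for everyone, so it does not average out across participants. The quantities directly at stake are time to onset and duration. Regimen attribution is at stake only if it too is read from the imputed date.

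**Working it through.** **Is weekly spacing realistic?** Inputs are from the Protocol synopsis (Treatment Groups and Duration): screening up to 28 days, minimum 7 days between doses, follow-up 7 to 9 days after the last dose.

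- Part A, 6 periods: 28 + 5 × 7 + (7 to 9) = 70 to 72 days, or 10.0 to 10.3 weeks. This reproduces the lower end of the stated 10 to 12 weeks.
- The 12-week limit, with the full 28-day screening, gives gaps of (84 − 28 − 9)/5 = 9.4 to (84 − 28 − 7)/5 = 9.8 days.
- Part B, 7 periods: 28 + 6 × 7 + (7 to 9) = 77 to 79 days, or 11.0 to 11.3 weeks. The 14-week limit gives gaps of (98 − 28 − 9)/6 = 10.2 to (98 − 28 − 7)/6 = 10.5 days.

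**When does the imputed onset precede the AE's own dose?** In Period 1 never, because the floor is that dose. In Period 2 or later the floor does not help. The imputed date reaches the AE's own dose date only if a first of the month falls between that dose and the onset, both days included. For onset *o* days after the dose that span is *o* + 1 days. With the first-dose date equally likely on any day of the year and 12 firsts of the month in 365 days:

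P(imputed onset before own dose) = 1 − 12(*o* + 1)/365.

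**6 periods, 7-day spacing, AEs equally likely in each period:**

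- Onset on the dosing day or the next 2 days: the mean of *o* + 1 is 2, so 1 − 24/365 = 93.4% in Periods 2 to 6. Over all six periods: 5/6 × 93.4% = 77.9%.
- Onset uniform over the interval: the mean of *o* + 1 is 4 in Periods 2 to 5, giving 1 − 48/365 = 86.8%. For Period 6, taking 8 days to follow-up, the mean is 4.5, giving 1 − 54/365 = 85.2%. The average over Periods 2 to 6 is (4 × 86.8% + 85.2%)/5 = 86.5%. Over all six periods: 5/6 × 86.5% = 72.1%.

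Enumeration over all 365 first-dose dates agrees with these values.

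**Sensitivity** (first figure: onset uniform over the interval; second: onset in the first 3 days):

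| Periods | Gap | Imputed onset before own dose |
|---|---|---|
| 4 (Part A, Periods 5 and 6 cancelled) | 7 d | 65% to 70% |
| 6 | 7 d | 72% to 78% |
| 6 | 10 d | 69% to 78% |
| 7 | 7 d | 74% to 80% |
| 7 | 10 d | 71% to 80% |

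With 6 periods, the share for uniform onset is still 57% at 21-day gaps and reaches 49% only at 28-day gaps.

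**If regimen were read from the imputed date** (last dose on or before it), the same shares would be credited to an earlier regimen and none to a later one. With 6 periods, 7-day gaps and onset uniform over 7 days, 22.1% + 14.5% + 5.8% + 0.2% = 43% would move by two or more regimens.

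**With the floor at the dose date of the recorded period**, the share is 0%.

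**The case against.** **The SAP does not say that regimen comes from the imputed date.** This stands. Section 10.7.2.1 names time to onset and duration as its purpose. Its only other stated use is the Appendix 4 status, and Appendix 4 defines phases and a treatment-emergent flag, not regimen. AE displays follow sponsor data standards (SAP 7.1) that are not in the documents and may use a recorded period. A reader might infer that most partially dated AEs will be tabulated under the wrong regimen; the documents support that only conditionally.

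**The floor can be read at period level.** If the start of study treatment meant the current period's dose, the problem would vanish. Appendix 4 does turn to period dates for later periods, but only for worsening AEs and under a different term. The study-level reading is therefore the more natural one, and the text should settle it.

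**Few AEs will be affected.** This also stands. Participants are resident to 48 hours after each MR dose (24 hours after the Part A IR dose), and Protocol Appendix 4 has the date and time of onset recorded. Month-only dates are least likely for events just after dosing, so the 78% end describes the less plausible cases. Washout and follow-up events are likelier candidates, and visits are about weekly.

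**The objective is not safety by regimen.** Correct. The objective is the safety and tolerability of single doses, summarised descriptively. Partial dates are also displayed as captured in listings, so an affected AE stays visible there.

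**Conclusion.** The rule as worded does not fit this design. For an AE with a missing start day, the imputed onset precedes the dose of its own period in about 72% to 78% of cases (6 periods, 7-day spacing), and in 65% to 80% across the number of periods and the 7- to 10-day gaps tabulated. Time to onset and duration are then wrong, always through too early an onset. This rests on four assumptions: the study-level reading of the floor, AEs spread evenly over periods, the two onset patterns shown, and a first-dose date equally likely on any day of the year.

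Misattribution to an earlier regimen follows only if regimen is derived from the imputed date. That is an inference from the lack of any other rule. The percentages apply to a count that the documents do not give and that is probably very small, so they do not show a material distortion of the safety results. This is a minor, inexpensive correction.

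**What to change.** In SAP 10.7.2.1, replace the start-day rule with wording such as: if the start day is missing, impute the later of the first of the month and the dose date of the treatment period in which the AE was recorded; regimen is taken from the recorded period and not from the imputed date; if no period is recorded, list the AE as having uncertain regimen attribution.

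For AEs with no recorded period, do not fall back on the latest dose in the month. With 6 doses 7 days apart, and a stop date that does not narrow the choice, that rule assigns 67% to 72% of such AEs to a later regimen. It is also undefined in 0.5% to 1.6% of cases, where the onset month contains no dose. It would largely reverse the error.

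The cost is a short change to the SAP text, a small programming change and a flag in the AE listing. It depends on the period being available in the AE record, which should be confirmed against the eCRF.
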